## **List of Abbreviations**

AE	Adverse Event/Adverse Experience
CFR	Code of Federal Regulations
CRF	Case Report Form
DSMB	Data and Safety Monitoring Board
FDA	Food and Drug Administration
GCP	Good Clinical Practice
HIPAA	Health Insurance Portability and Accountability Act
IB	Investigator's Brochure
IND	Investigational New Drug Application
IRB	Institutional Review Board
PHI	Protected Health Information
PI	Principal Investigator
SAE	Serious Adverse Event/Serious Adverse Experience
SOP	Standard Operating Procedure
cDVT	Calf deep vein thrombosis

## Study Summary

Title	A Phase IV, Randomized, Double Blind Placebo controlled Study Evaluating the Safety and Efficacy of Apixaban in Subjects with Isolated Calf Vein Thrombosis
Running Title	Golden Calf Trial
Protocol Number	17-009022
Phase	Phase IV
Methodology	Single center, multi-Mayo site randomized, double blind, placebo-controlled, superiority clinical trial.
Overall Study Duration	36 months
Subject Participation Duration	Each individual will be in the study for 3 months
Single or Multi-Site	Single center, multi-Mayo site Trial
Objectives	There are two primary objectives. The first primary objective is to evaluate whether a strategy of active anticoagulation with apixaban is more efficacious than no anticoagulation (i.e., placebo) when monitored with serial ultrasound imaging in the management of patients with isolated calf vein thrombosis (DVT) for the composite endpoint consisting of prevention of thrombus propagation, pulmonary embolism, recurrent venous thromboembolic events, and all cause mortality. The second primary objective, safety, is to assess the combination of major and clinically relevant non-major bleeding for subjects randomized to apixaban vs. placebo control.
Number of Subjects	The number of patients needed is 250, or 125 in each of the two treatment arms.
Diagnosis and Main Inclusion Criteria	Patients will be recruited for study participation if they have a newly diagnosed venous thrombotic event (DVT) limited to the calf veins.
Study Product, Dose, Route, Regimen	Apixaban (10 mg twice daily for 7 days followed by 5 mg twice daily for 3 months) or matching placebo.
Duration of Administration	Total duration of drug administration will be for the duration of study participation 3 months.
Reference therapy	Serial clinical monitoring as is standard of practice with matching placebo. All patients will undergo serial ultrasound imaging at day 7, day 14, and day 90.
Primary Endpoint	Combined endpoint including thrombus propagation, pulmonary embolism, recurrent venous thromboembolism, and all cause mortality over three months.

Sample Size Estimation	An anticipated venous thromboembolic event rate of 10.0 to 12.6% within 3 months for patients randomized to standard medical observation and placebo is expected. We hypothesize the apixaban arm will result in a 3 month event rate of 1.0% to 2.3%. At an interim-analysis alpha level of 0.049 and events rates of 10% and 1.6% for placebo and apixaban, respectively, a sample size of 121/gp is required to achieve 80% power. To account for minor attrition over the course of the study, 125/gp or 250 total is planned for target enrollment.
Statistical Methodology	The primary outcome measure will be tested using a Cochran-Mantel-Haenszel chi-square with clinical site considered as a stratification variable. The pooled estimate of the odds ratio will be used as the primary measure of effect. The study is designed with an interim analysis with an information fraction of 40%. The O'Brien-Fleming alpha spending function will be used to provide control over the type I error rate.

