## 1.1 Background

Venous thromboembolism (VTE) represents a major cause of morbidity and mortality in the USA.(1–3) The incidence of VTE exceeds 1 per 1000 with as many as 600,000 first life-time cases diagnosed annually in this country. The 7 day mortality of patients suffering a thrombotic event is 25% and up to 35% of patients with pulmonary embolism (PE) die suddenly. Venous thromboembolism is therefore the fourth leading cause of death in Western society and the third leading cause of cardiovascular death behind myocardial infarction and stroke. Furthermore, VTE is both a recurrent disease and a morbid disease. Of those individuals surviving the thrombotic event, 30% will develop recurrent venous thromboembolism within 10 years and 20–30% will develop the post-phlebitic syndrome over this time period. VTE is typically a disease of elderly people, with the incidence of thrombotic events increasing significantly beyond age 60. As our population ages, the expected number of VTE annually will increase. Despite advances in radiographic detection, expanded knowledge of risk factors, and anticoagulant development, the incidence of VTE has been relatively constant over the past several decades.

Isolated cDVT accounts for nearly half of all DVTs occurring the United States each year (7). As such, as many as 300,000 cases annually require thoughtful management (1,7). And yet, there is very little high quality data to guide clinicians managing these patients. Indeed, the precise incidence of cDVT in the community is not well established. It is felt that the embolic potential of cDVT left untreated is low and embolization risk only increases with thrombus propagation to the popliteal vein or higher. The risk of proximal propagation if untreated ranges from 2 to 23% and likely varies by the clinical context (6). Cancer, recent surgery, hospital confinement, prior history of VTE and large thrombus size are said to be risk factors for thrombus propagation (5). These factors are derived from different cohorts and do not necessarily deserve the same weighting in a risk assessment strategy. A dedicated risk stratification tool would be immensely helpful to identify those individuals most likely to benefit from anticoagulation therapy however such a tool does not exist.

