Managing cDVT is therefore particularly challenging for a number of reasons. First, there are few community based epidemiology cohort studies to assess risk factors for cDVT. Second, there is a dearth of information regarding the natural history of this disease. Many studies combine deep veins and muscular veins together under the same category yet these veins are not anatomically similar and likely carry very different embolic and thrombotic propagation propensity. Third, there is a paucity of strong clinical trial data to help guide treatment decisions. Many of the prominent clinical trials excluded cDVT as an entry event. Disparity exists across institutions regarding management protocols. Indeed, many institutions don't mandate calf vein imaging as part of their ultrasound protocol. It is the practice in some clinicians to provide full anticoagulant therapy for patients with cDVT for three months. Other clinicians pursue serial imaging over 2 to 3 weeks and only provide anticoagulant therapy if there is evidence of thrombus propagation to the popliteal vein, embolization to the pulmonary vasculature or symptomatic recurrent venous thrombosis in other locations. Both camps would point to small studies to support their approach. The most appropriate strategy however remains unclear given the lack of strong data.

There have been 6 treatment trials of isolated cDVT (7,11-15). Trial sizes ranged from 32 to 259 patients with a total randomized in all six trials combined of 711 subjects (Table 1). Treatment varied from serial observation to full anticoagulation with warfarin. Treatment duration varied from 10 days to 3 months.

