Based on these treatment trials, guideline recommendations for patients with cDVT include a preference for serial ultrasound evaluation with observation over anticoagulation therapy in the absence of severe symptoms, active cancer, hospitalized status, prior history of VTE, unprovoked event, multiple venous involvement or large thrombus size ( $> 7$  mm width and or  $> 5$  cm length) or positive fibrin D-Dimer (5). This approach however has **several disadvantages**. **First**, if untreated patients participating in the randomized trials and cohort studies are combined, the anticipated event rate for untreated VTE is relatively high at 11.2% at 3 months (7,12,14,15,17). This includes a DVT propagation rate of 4.8%, PE rate of 1% and VTE recurrence rate of 5.4%. These event rates are high by comparison to patients with unprovoked

proximal DVT or PE. For unprovoked proximal DVT or PE, the event recurrence rate is approximately 8% at one year and 30% at 5 years. For these unprovoked VTE, there is universal agreement that continued anticoagulation therapy is indicated (Grade 1A) (5). If the latter deserves ongoing anticoagulant therapy then cDVT should deserve consideration for anticoagulant therapy as well. **Second**, the reason for avoiding anticoagulant therapy is said to be due to increased rate of major bleeding. In the CACTUS trial, this rate was acceptably low at 0.8% (15). In the trial by Ferarra et al, there were no major bleeding events despite enrollment confined to post-operative patients (13). **Third**, the post thrombotic syndrome following cDVT is said to be low however this has not been adequately studied and no firm conclusion can yet be established. **Fourth**, cDVT was specifically excluded from the recent large randomized trials of DOACs. **Fifth**, serial ultrasound does nothing for VTE prevention. Timing the interval to 7 days between studies may place the patient at considerable risk of thrombotic propagation and embolization which may prove to be a life threatening event. For these combined reasons, a prospective randomized trial of anticoagulant therapy compared to serial ultrasound imaging strategy is necessary and important. Given the vast number of patients suffering calf DVT each year in our society, establishing the most appropriate treatment strategy is paramount.

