### **5.4.1 Stratification**

Prior to randomization, subjects will be stratified on thrombotic risk based on the presence of one or more of the following characteristics: deep vs. muscular venous thrombosis, postoperative status, and single vs. multiple venous segment involvement.

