### **5.8.1 Receipt of Drug Supplies**

The BMS/Pfizer will provide bulk drug supply to McKesson. McKesson will then package drug pre-labeled by assigned randomization bottle numbers in bottles containing 200 tablets of either apixaban or matching placebo to each site. Upon request, each site will then be supplied with drug in bottles, along with a shipment manifest of the total bottle numbers dispensed. Upon receipt of drug from McKesson, each Mayo Clinic Pharmacy site will coordinate the dispensing of the blinded randomized treatment to study coordinator. Upon receipt of the study treatment supplies, an inventory must be performed and a drug receipt log filled out by the person accepting the shipment at MCP. The designated study staff will count and verify that the shipment contains all the items noted in the shipping invoice. Any discrepancies, damaged or unusable study drug in a given shipment (active drug or comparator) will be documented in the study files. The sponsor-investigator will be notified immediately of any discrepancies, damaged or unusable products that are received. Delegated unblinded study staff will have access to the randomization key. Through use of a Mayo licensed randomization software, the bottle numbers will be assigned to the designated site at the time of randomization using the stratification outlined in 5.4.1.

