## 7.2 Statistical Methods

### 7.2.1 Primary Hypothesis:

We hypothesize that apixaban 5 mg twice daily is associated with a significantly lower rate of the primary composite efficacy outcome compared to matched placebo in patients with calf DVT.

**7.2.1.2 Primary Efficacy Analysis:** All patients randomized to receive at least one dose of apixaban 5 mg or matching placebo control will be included in the primary analysis under intention to treat (see analysis sets below). The analysis of the primary composite endpoint will only include events occurring during the 3 months of study medication use.

Frequency of the primary composite efficacy endpoint will be tabulated by treatment arm without regard to the time the event was observed within the 3 month study period. The Cochran-Mantel-Haenszel test will be used to compare the event rates by treatment group. The pooled estimate of the odds ratio will be used as the primary measure of association for the study.

An exploratory analysis will investigate the time to event is defined as the time from randomization to the first occurrence of a primary composite efficacy outcome event. Patients who were lost to follow-up or who withdrew consent before the end of the three month treatment period will be censored at the last day the patient had a complete assessment for study outcomes within the 3 month study period. The incidence curves of VTE events will be plotted using the Kaplan-Meier estimator by treatment group. The difference in the incidences of the primary composite outcome at 3 months between treatment arms will be estimated and tested using a normal approximation of the binomial distribution.

**7.2.1.3 Safety Analysis:** All patients who received at least one dose of study medication will be included in the safety analysis. The analysis of major bleeding and clinically relevant non-major bleeding events will include those events which occurred during the 3 month study period. Major bleeding events observed later will be described separately.

Frequency of major bleeding and clinically relevant non-major bleeding will be tabulated by treatment arm. The incidence of major bleeding and clinically relevant non-major bleeding will be summarized as a combined endpoint and separate endpoints by treatment arm. The difference in the incidences of the combined endpoint at 3 months between treatment arms will be estimated and tested using a normal approximation of the binomial distribution.

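### The primary Cochran-Mantel-Haenszel test and pooled odds ratio leave out the thrombotic-risk strata used to randomise; adding them is a cheap, small improvement

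*Combined protocol and SAP*

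**What the plan says.** - **Randomisation.** Section 5.4.1: "subjects will be stratified on thrombotic risk based on the presence of one or more of the following characteristics". It lists three: deep versus muscular vein, postoperative status, and single versus multiple segments. Site is not listed. Section 5.8.1 confirms how this is applied: "the bottle numbers will be assigned to the designated site at the time of randomization using the stratification outlined in 5.4.1".
- **Primary analysis.** The Study Summary has the primary outcome "tested using a Cochran-Mantel-Haenszel chi-square with clinical site considered as a stratification variable". Section 7.2.1.2 says "The Cochran-Mantel-Haenszel test will be used to compare the event rates by treatment group" and "The pooled estimate of the odds ratio will be used as the primary measure of association for the study". It names no stratifier.
- **Prognostic value.** Section 1.1 says of deep and muscular veins that "these veins are not anatomically similar and likely carry very different embolic and thrombotic propagation propensity". On surgery it says: "Cancer, recent surgery, hospital confinement, prior history of VTE and large thrombus size are said to be risk factors for thrombus propagation". Its list of guideline factors that weigh against observation alone includes "prior history of VTE, unprovoked event, multiple venous involvement or large thrombus size". None of these statements comes with an effect size.

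No section carries the risk strata into the primary test or the odds ratio.

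**The concern.** Stratified randomisation balances the arms on the strata. If the strata predict outcome, that balance removes between-stratum variation from the treatment comparison. A test that ignores the strata still counts this variation as noise, so its true type I error falls below nominal and some power is lost. With about 14.5 expected events (125 × 10% + 125 × 1.6%), it is reasonable to ask how much.

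There is also a gap in definition. A Cochran-Mantel-Haenszel test and a pooled odds ratio are fixed only once the strata are named, and only the Study Summary names any. The wording of 5.4.1 can mean one high/low variable or up to eight crossed cells, so the randomisation strata cannot be reconstructed from the text.

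**Working it through.** **1. The plan's own figure.** Inputs from section 7.1: 10.0% versus 1.6%, two-sided alpha 0.0492 (z = 1.967), power 80% (z = 0.842), no continuity correction. The mean rate is 5.8%.

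n = [1.967·√(2·0.058·0.942) + 0.842·√(0.10·0.90 + 0.016·0.984)]² / 0.084² ≈ 121 per arm.

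This matches the stated 121. Power by this formula is 81.3% at 125 per arm. The calculation is an unstratified two-group comparison, so it never relied on the risk strata.

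**2. Type I error with the strata left out (large-sample).** Actual size = 2[1 − Φ(1.967/√R)], where R is the within-stratum variance divided by the total binomial variance. With two equal risk groups at 4% and 16% (assumed):

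R = ½(0.04·0.96 + 0.16·0.84)/(0.10·0.90) = 0.0864/0.09 = 0.96, so size = 2[1 − Φ(2.007)] = 4.5%.

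At 7% and 13%, R = 0.0891/0.09 = 0.99 and size = 4.8%.

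**3. Simulation.** Settings: 40,000 trials per scenario, 250 participants, and sites 60/20/20 (from the targets of 150/50/50 in section 5.5). Assumed: permuted blocks of 4 within risk stratum, equal risk groups except in the last row, and site not prognostic. Apixaban relative risk is 1 or 0.16, and the final test is at 0.0492. Simulation error is about 0.1 point for type I error, 0.2 for power and 0.1 for paired differences.

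| Placebo rate, low/high risk | Odds ratio | Type I error, site / risk (%) | Power, site / risk (%) |
|---|---|---|---|
| 10 / 10 | 1.0 | 4.7 / 4.6 | 85.6 / 85.7 |
| 8.5 / 11.5 | 1.4 | 5.0 / 4.9 | 85.1 / 85.3 |
| 7 / 13 | 2.0 | 4.7 / 4.8 | 85.8 / 86.0 |
| 4 / 16 | 4.6 | 4.3 / 4.8 | 86.0 / 86.7 |
| 5 / 30 (80:20 mix) | 8.1 | 3.6 / 4.8 | 85.8 / 87.6 |

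A separate run of 10,000 trials gave 4.4% versus 4.8% and 86.0% versus 86.7% at 4/16, and no resolvable difference at 7/13 (power 85.6% both ways). Another, of 20,000, gave a 0.4-point loss at 7/13, which is within simulation error of the table. Simulated power exceeds the 81.3% of the formula; only the differences matter here.

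**4. If site is prognostic instead (assumed).** With placebo rates of 15/2.5/2.5% by site and risk not prognostic, power is 86.6% stratified by site and 85.6% by risk. At 4/19/19% it is 86.3% and 85.4%. At 12/7/7% it is 86.1% and 85.9%.

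**5. Using both.**
- High/low risk crossed with site (6 cells) stays within −0.5 to +0.7 points of the site-stratified test over 13 scenarios; its lowest power is 84.9%.
- Eight risk cells alone give 85.7% to 87.3% (site 85.4% to 86.0%) if site is not prognostic, and 85.8% to 86.2% (site 86.5% to 86.7%) at 15/2.5/2.5%.
- Eight cells crossed with three sites are too sparse: 82.8% to 83.4%.

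**6. Interim look.** With 100 participants at p < 0.00079, the chance of crossing is 0.5% to 0.9% by site and 0.6% to 1.1% by 6 cells. The choice hardly matters there.

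**7. What the documents offer on strength.**
- Untreated propagation was 3.8% in the muscular-vein trial and 5.3% in the largest all-comers trial (table in section 7.1). The odds ratio is (0.053/0.947)/(0.038/0.962) = 1.4. It compares different trials, and the 3.8% is two patients per group.
- The post-operative trial in the same table shows 14% for single-vein and 9% for multiple-vein disease. The odds ratio is (0.14/0.86)/(0.09/0.91) = 1.6 in the opposite direction. Those patients were treated, and the durations shown differ.

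**The case against.** The strongest reply is that nothing planned is harmed and site is a sensible stratifier in a three-site trial. Much of this stands. At the strength the documents hint at, simulation resolves no conservatism, and the power difference is a few tenths of a point. The last row of the table puts only 20% of patients at high risk. If high risk means any one of three factors, with assumed independent prevalences of 50%, 25% and 35%, about 76% would be high risk (1 − 0.50·0.75·0.65). With that mix, an odds ratio of 4.5 loses only 0.4 points. Section 1.1 also says that the risk factors come from different cohorts and may not merit equal weight. It speaks of multiple veins, whereas 5.4.1 speaks of multiple segments.

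Replacing site outright is not free either: it costs about 1 point if site is strongly prognostic. That is a reason to add the risk strata where the cell count allows, not to leave them out.

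A reader might infer that the Study Summary and 7.2.1.2 contradict each other. They do not: 7.2.1.2 is silent. A reader might also infer an inflated type I error or an underpowered trial. Omitting balanced strata pushes the test towards conservatism, and simulated power stays above 80% throughout.

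**Conclusion.** The mismatch is real: the primary analysis omits the randomisation strata. Its effect is small. With strongly prognostic strata (4% and 16%, assumed), type I error is about 4.4% instead of 4.92% and about 0.7 points of power are lost. At an odds ratio of 2 or less, the loss is about 0 to 0.3 points; if the strata are not prognostic there is essentially none. The sizes depend on assumed rates, prevalences and block size, because the documents supply no reliable effect size and their two rough comparisons are weak. It would go too far to say that the documents show these factors to be prognostic, or that the conclusion of the trial is at risk. This is a cheap improvement, not an error that changes the conclusion.

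**What to change.** - In 5.4.1, state whether the randomisation system holds one high/low variable or crossed cells.
- In the Study Summary and 7.2.1.2, include those strata, as coded at randomisation, in the primary test and pooled odds ratio. Use the same definition at the interim look.
- If there is one high/low variable, cross it with site (6 cells). This keeps the site adjustment at little or no cost.
- If there are eight cells, stratify by them alone, do not cross them with site, and keep the site-stratified test as a sensitivity analysis.

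The cost is wording in three places. No new data are needed, because the strata are recorded at randomisation. The downside of the eight-cell route is up to about 1 point of power if site is strongly prognostic, still well above 80%.

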## 1 Introduction

This document is a protocol for a human research study. This study will be carried out in accordance with the applicable United States government regulations and Mayo Clinic research policies and procedures.

Each year, between 300,000 to 600,000 individuals suffer an acute venous thromboembolic event (1-4). These events primarily involve the deep veins of the lower extremities (deep vein thrombosis, DVT) which may lead to embolization to the pulmonary arteries (pulmonary embolism, PE). Deep vein thrombosis of the lower extremity is divided into two categories depending on the proximal extent of thrombosis. Thrombi involving the popliteal, femoral and iliac veins are categorized together into "proximal DVT" largely due to their increased embolic potential. Indeed, the risk of embolization of proximal DVTs may be as high as 50% (3). Whereas the risk of mortality associated with a PE is high, prompt identification and treatment initiation with anticoagulants is a medical emergency. Both the evaluation and management of proximal DVT and PE has been well established by randomized controlled trial data (5).

In contrast, the management of venous thrombi limited to the calf veins is not well established (6). "Distal" deep vein thrombosis involve either the deep (posterior tibial, peroneal calf, and anterior tibial) or muscular (soleal and gastrocnemius) veins of the calf but do not extend into the popliteal veins. These "calf vein thrombi" (cDVT) are numerous and account for half of the DVT burden in a community setting (150,000 – 300,000 events annually in the United States) (7). While the likelihood of embolization is low, propagation of calf vein thrombi to the popliteal vein greatly augments the PE risk. Prevention of thrombus propagation can be readily accomplished with anticoagulation therapy however this therapy comes with a small risk of major hemorrhage (8). As such, management strategies vary considerably across sites with some investigators advocating conservative ultrasound surveillance without anticoagulation while others recommend full anticoagulant therapy for three months. There are few adequately powered randomized controlled trial data to guide management of these patients. The guidelines recommend serial ultrasound imaging for 2 weeks over anticoagulation therapy unless symptoms are severe or there are risk factors for thrombus extension (5). These guidelines are problematic for several reasons. First, the weight of the recommendation is based on expert opinion only (Grade 2C) and second, validated risk prediction tools for thrombus propagation do not exist (9). Current guidelines also suggest anticoagulation if the thrombus extends but remains confined to the distal veins (Grade 2C). There are little data to support this latter recommendation. Recently, the FDA has approved an oral direct factor Xa inhibitor, apixaban, which has been shown to be a highly effective anticoagulant for VTE (10). This agent has a particular advantage in that it is associated with very low bleeding rates making this anticoagulant particularly attractive for the treatment of cDVT.

We propose a phase IV, randomized, double blind placebo controlled study evaluating the safety and efficacy of apixaban compared to observation with serial ultrasound imaging alone in subjects with acute venous thrombosis limited to the calf veins. The primary objective is to evaluate whether a strategy of anticoagulation with apixaban is more effective than serial ultrasound imaging in the management of patients

with cDVT for the prevention of thrombus propagation, pulmonary embolism and recurrent venous thromboembolic events.

